While both routes are safe and routinely used by cardiac anesthesiologists at UVA, there are several proposed advantages to nasal intubation in the neonatal cardiac population. Firstly, nasotracheal tubes are more comfortable to the patient as well as more easily secured. Because of this, thus patient requires less sedation to prevent accidental extubation. Secondly, without an oral endotracheal tube in place, the infant is able to practice non-nutritive sucking skills in preparation for oral feeding. A study by Pinelli et al. (2005) showed that non-nutritive sucking helped premature infants more quickly transition from gavage to oral feeding. With lower sedation and oral skills development, we believe that nasally intubated patients will more quickly learn to orally feed and avoid the need for gastrostomy.

Objectives/Hypothesis

Hypothesis: Nasotracheal intubation will allow for lighter sedation in the post-operative period as well as more rapid development of oral feeding skills for infants with congenital heart disease.

Primary outcome measures:

1) Time from surgery to full oral feeds.

Secondary outcome measures:

- 1) Dosage of sedating medications required post-operatively.
- 2) Hospital length of stay.
- 3) Need for tube feeds at discharge (NG or gastrostomy).

Study Design: Biomedical

1. Will controls be used?

No. Participants will be randomized to an intervention - either oral or nasal intubation. All infants will be intubated for surgery, so there is not a control group.

► **IF YES, explain the kind of controls to be used.**

Answer/Response:

2. What is the study design?

Randomized control study

3. Does the study involve a placebo?

No, participants will receive either oral or nasal intubation, both routes are considered safe and acceptable in neonates.

► **IF YES, provide a justification for the use of a placebo**

Answer/Response:

Human Participants

Ages: <2 weeks at the time of surgery

Sex: Male and female

Race: All

Subjects- see below

1. Provide target # of subjects (at all sites) needed to complete protocol.

Version Date: 06/14/18

Page Number: 3 of 8

A sample of 40 neonates in each group, for a total of 80 neonates, is required to have sufficient statistical power.

2. Describe expected rate of screen failure/ dropouts/withdrawals from all sites.

We anticipate that 10% of neonates will be unobserved on the primary outcome due to post-operative complications including need for ECMO or CPR >5 minutes.

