Preliminary data on 8 neonates yielded an average of 13.5 from surgery to NG tube removal, with a standard deviation of 11.7. With 40 participants per group, the two-sample t-test with unequal variances yields 80% power, with a 2-sided significance level of 5%, when the mean difference in time to oral feeding is 6 days. In this calculation, we assumed that the coefficient of variation is the same in the nasal and oral intubation groups, meaning that the within-group standard deviation is proportion to the mean. Allowing for 10% dropout/withdrawal yields a sample size of 44 per group, for a total of 88 participants.

4. What is your plan for primary variable analysis?

Initial analyses will use the two-sample t-test, and the associated confidence interval, to compare the groups. Secondary analyses of the primary outcome, the number of days until full oral feeding, will be based on negative binomial regression. In addition to providing an unadjusted comparison of the groups, the use of negative binomial regression will also allow us to estimate the difference between the groups adjusting for covariates, such as the RACHS score (estimates risk of cardiac surgery). While we anticipate that the randomization will balance the distribution of these covariates between the groups, the use of these covariates in a model can improve the precision in estimating the difference between the oral and nasal intubation groups.

5. What is your plan for secondary variable analysis?

A two-sample nonparametric test will be used to compare the average dosage of sedating medications required post-operatively. For hospital length of stay, analyses similar to those described above for days until full oral feeding will be used. The third secondary outcome is a binary variable, indicating the need for tube feeds at discharge. The chi-square tests will be used to compare the proportion of participants in each group requiring tube feeding at discharge.

6. Have you been working with a statistician in designing this protocol?

Yes

IF YES, what is their name?

[name]

7. Will data from multiple sites be combined during analysis?

No

INSTRUCTIONS: IF YES, answer the following questions

7(a). Does the study involve randomization?

Answer/Response:

IF YES, will randomization be done at each site or among sites?

Answer/Response:

7(b). Has the sample size calculation considered the variation among sites?

Answer/Response:

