longer time required for nasal intubation, then they will be orally intubated for patient's safety. These patients will remain in the study and will be analyzed in the oral intubation group. Intubation route does not affect the subsequent surgery.

The patient will arrive to PICU intubated. The electronic medical record will be used to collect data regarding surgical variables, post-operative sedation needs, and feeding outcomes. The treatment of these patients post-operatively will follow the standard of care PICU procedures, without differences based on study assignment. The post-operative protocols are described briefly here: Sedation needs are determined by standardized sedation scores and nursing protocols. Feeding advances are determined by standardized PICU protocol, with alterations based on RN and MD clinical assessment. The patient will be extubated when clinically appropriate, based on PICU MD assessment. After extubation, the patient is assessed by a Speech-Language Pathologist who determines the patient progress with oral feeding. Data will be collected through hospital discharge.

2. If this protocol involves study treatment, explain how a subject will be transitioned from study treatment when they have completed their participation in the study.

This protocol does not involve an experimental treatment. Both oral and nasal intubation are safe methods, and both are routinely used by the pediatric cardiac anesthesiologists at UVA. After intubation, the remainder of the infant's intra- and post-operative care will proceed by the standard of care. The subject will be extubated when clinically appropriate as determined by the PICU MD. If the patient requires emergent re-intubation while in the PICU, it will be performed orally. Patients who are re-intubated will remain part of the study as long as they do not meet other exclusion criteria (ex. Intubated >2 weeks, >5 min CPR, ECMO).

Subject Compliance with Study Procedures

1. Explain how the study team will monitor the subject for compliance with the study procedures.

The study anesthesiologists will perform the procedure. There is no need for the patient or family to comply.

2. Describe criteria for when a subject is considered to be non-compliant with study procedures.

There is no need for the patient or family to comply. All procedures are performed by the study team.

Bibliography

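### Does the sample-size statement leave its 80% power undetermined by giving a 6-day difference without the two arm means?

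*Protocol*

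**What the plan says.** Protocol, Statistical Considerations, item 3 (justification for the sample size) gives these planning inputs in one paragraph:

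- Pilot mean: "Preliminary data on 8 neonates yielded an average of 13.5 from surgery to NG tube removal".
- Pilot SD: "with a standard deviation of 11.7".
- Test and group size: "With 40 participants per group, the two-sample t-test with unequal variances yields 80% power".
- Error rate and effect: the calculation "yields 80% power, with a 2-sided significance level of 5%, when the mean difference in time to oral feeding is 6 days".
- Variance model: "we assumed that the coefficient of variation is the same in the nasal and oral intubation groups".
- Allowance for loss: "Allowing for 10% dropout/withdrawal yields a sample size of 44 per group, for a total of 88 participants".

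On direction, the Background says "we believe that nasally intubated patients will more quickly learn to orally feed". On current practice, Study Procedures, item 2 says of the two routes that "both are routinely used by the pediatric cardiac anesthesiologists at UVA". The protocol does not state the route of the 8 pilot infants and does not print an assumed mean or SD for either arm.

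**The concern.** With a common SD, a difference and an SD are enough to fix the power of a t-test. This protocol lets the SD grow with the mean, so the same 6 days is easier to detect when both means are low than when both are high. Power then depends on where the two means sit, and the paragraph names only their difference. A reader may suspect that the 80% cannot be traced to its inputs.

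The suspicion has some substance. Both routes are in routine use at the centre, so the pilot series might have contained both. If so, 13.5 days would be an average over routes and not the mean of the slower arm, and power for 6 days would be lower. A null result might then come from a trial able to detect only a larger difference than the one advertised.

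Two smaller points add to the impression. The pilot variable is time to NG tube removal, while the endpoint is time to full oral feeds. And 44 per group is 40 × 1.10, not 40/0.90.

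**Working it through.** **Inputs** (all from Protocol, Statistical Considerations, item 3): pilot mean 13.5, pilot SD 11.7, n = 40 per group, two-sided 5%, difference 6 days, unequal-variance t-test, equal coefficient of variation (CV) in both arms.

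**Formulas.** CV = 11.7/13.5 = 0.867, and each arm's SD = CV × its mean. SE = √[(SD₁² + SD₂²)/n]. The noncentrality is 6/SE. Power comes from the noncentral t distribution with Satterthwaite degrees of freedom.

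**The protocol's own figure.** Take 13.5 as the slower arm and subtract 6 days:

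- Means 13.5 and 7.5; SDs 11.7 and 0.867 × 7.5 = 6.5.
- SE = √[(136.89 + 42.25)/40] = √4.479 = 2.116.
- Noncentrality = 6/2.116 = 2.835, with 61 degrees of freedom.
- Power = **79.7%** (80.9% by the normal approximation).

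The stated 80% is reproduced.

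**Could another pair of means have produced it?** Same CV, n = 40 per group, means 6 days apart:

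| Means (days) | SDs | SE | Power |
|---|---|---|---|
| 13 vs 7 | 11.27, 6.07 | 2.023 | 83.1% |
| 13.5 vs 7.5 (pilot = slower arm) | 11.7, 6.5 | 2.116 | 79.7% |
| 14 vs 8 | 12.13, 6.93 | 2.210 | 76.2% |
| 16.5 vs 10.5 (pilot = midpoint) | 14.3, 9.1 | 2.680 | 59.7% |
| 19.5 vs 13.5 (pilot = faster arm) | 16.9, 11.7 | 3.250 | 44.5% |

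With the difference and CV fixed, raising both means raises both SDs, so power falls steadily down the table. Only one pair can give a particular power, and the pair for 80% is the one anchored on the pilot mean as the slower arm. A common SD of 11.7 in both arms gives 62.0%, so the constant-CV statement was also used as described. For the pair 13.5 vs 7.5, 80% power is reached at 41 per group by this method and at 40 by the normal approximation.

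**If the pilot had been a mix of routes.** This is an assumption; the protocol does not say so. With a fraction p of the pilot infants on the slower route and the arms 6 days apart, the means are 13.5 + 6(1 − p) and 13.5 − 6p. The lower power in each row keeps CV 0.867; the higher one first removes the between-route variance from the pilot SD.

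| p | Means (days) | Power |
|---|---|---|
| 0.25 | 18.0 vs 12.0 | 51 to 55% |
| 0.50 | 16.5 vs 10.5 | 60 to 65% |
| 0.75 | 15.0 vs 9.0 | 69 to 73% |
| 1 (all on the slower route) | 13.5 vs 7.5 | 79.7% |

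For p = 0.50 the adjusted CV is √[(11.7² − 3²)/((16.5² + 10.5²)/2)] = √(127.89/191.25) = 0.818. The difference detectable with 80% power is then 7.1 to 7.7 days, against 6.0 days when 13.5 is the slower arm. These figures depend on p, for which the protocol gives no value.

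**Allowance for loss.** 40 × 1.10 = 44 and 40/0.90 = 44.4. A 10% loss from 44 leaves 44 × 0.90 = 39.6 per group, and power at 13.5 vs 7.5 moves from 79.7% to 79.3%.

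**The case for a change.** The strongest case for the concern is that the justification makes power depend on the arm means and then leaves them out. The reader has to infer that 13.5 is the slower arm. The hypothesis test is two-sided, so the paragraph itself fixes no direction. Because both routes are routine at this centre, a mixed pilot is plausible, and in that event the trial would be weaker than stated. The sponsor knows the pilot infants' routes and could settle the matter in two or three sentences.

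Part of this stands. The means are not printed, the pilot route is not given, and a fuller paragraph would have included both. The rest does not make a fault:

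- The inference is not a guess. Only one placement of 13.5 returns the stated 80%, and it is the one that agrees with the Background's expectation of faster feeding with nasal intubation.
- The protocol says that both routes are used at the centre, not that the pilot contained both. If all 8 infants had the slower route, there is no shortfall. No single lower figure can be defended, since the mixed-pilot result runs from about 51% to 73% over the splits shown.
- A null result would be read from the confidence interval that item 4 plans alongside the t-test, not from planning power.
- The pilot variable is openly named as time to NG tube removal in the sentence that supplies the inputs, so its use as a stand-in is disclosed.

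**Conclusion.** The concern does not hold. The stated 80% is correct on the protocol's own inputs (79.7%), and that figure identifies the pair of means behind it: 13.5 vs 7.5 days, with SDs 11.7 and 6.5. What remains is a preference for printing numbers that can already be derived. Printing them would leave enrolment, conduct and analysis as they are. The rounding in the allowance for loss costs 0.4 percentage points (79.7% to 79.3%).

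This conclusion rests on reading 13.5 days as the slower arm, which the arithmetic and the Background both support. It would need another look only if the pilot infants turned out to be a mix of routes, and nothing in the protocol says that they were.

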3. How many subjects will be enrolled at all sites?

44 participants per group, for a total of 88

4. How many subjects will sign a consent form under this UVa protocol?

88 participants.

Inclusion/Exclusion Criteria

1. List the criteria for inclusion

- Patient is a neonate requiring cardiac surgery
- Patient is <2 weeks of age at the time of surgery
- Includes families who are educationally or economically disadvantaged
- Includes non-English speaking families

2. List the criteria for exclusion

- Patient has an estimated gestational age <37 weeks at the time of surgery
- Patient has known oro-facial or gastrointestinal anomalies
- Patient has known congenital or acquired devastating neurologic injury
- Patient was intubated for >5 days pre-operatively
- Patient required >5 minutes of CPR pre- or post-operatively
- Patient requires ECMO pre- or post-operatively
- Patient remains intubated two weeks post-operatively.
- Excludes infants >2 weeks of age at the time of surgery and other vulnerable populations including pregnant women, fetuses, prisoners, cognitively impaired

3. List any restrictions on use of other drugs or treatments.

None.

Statistical Considerations

1. Is stratification/randomization involved?

Yes.

► IF YES, describe the stratification/ randomization scheme.

Patients will be randomized to oral or nasal intubation using a block randomization scheme generated by a UVA statistician to generate equally sized oral and nasal groups. The concealment envelope with group assignment will be opened by the anesthesiologist, CRNA, or resident performing intubation at the time of surgery. After intubation, this intervention is impossible to blind. The research team and family will be able to see which group the patient is part of.

► IF YES, who will generate the randomization scheme?

Sponsor
 UVa Statistician. [name]
 UVa Investigational Drug Service (IDS)
 Other: Answer/Response:

2. What are the statistical considerations for the protocol?

The null hypothesis to be tested is that the mean number of days to full oral feeding is the same with oral or nasal intubation. The alternative hypothesis is two-sided, and states that the mean number of days until full oral feeds differs between oral and nasal intubation.

3. Provide a justification for the sample size used in this protocol.

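### The planned 88 infants, less the expected 10% loss, leave about 79 evaluable, just under the 80 the protocol says it requires

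*Protocol*

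**What the plan says.** Four statements in the protocol bear on this point.

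- Human Participants, Subjects item 1, gives the number needed: "A sample of 40 neonates in each group, for a total of 80 neonates, is required to have sufficient statistical power".
- Subjects item 2 gives the expected loss: "We anticipate that 10% of neonates will be unobserved on the primary outcome due to post-operative complications including need for ECMO or CPR >5 minutes".
- Subjects item 3 gives enrolment: "44 participants per group, for a total of 88". Item 4 repeats 88 as the number who will sign consent.
- Statistical Considerations item 3 links them: "Allowing for 10% dropout/withdrawal yields a sample size of 44 per group, for a total of 88 participants".

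The same item 3 gives the basis for the 40. "Preliminary data on 8 neonates yielded an average of 13.5 from surgery to NG tube removal, with a standard deviation of 11.7". With 40 per group, "the two-sample t-test with unequal variances yields 80% power, with a 2-sided significance level of 5" per cent, "when the mean difference in time to oral feeding is 6 days". It adds that the coefficient of variation is taken as equal in the two groups. Neither the inflation formula nor a rounding rule is shown.

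**The concern.** Item 2 defines the 10% as a share of neonates who will contribute no primary outcome. The 40 per group in item 1 is therefore the number that must remain after the loss, and enrolment should be large enough that 90% of it is at least 40. Forty-four is not quite large enough.

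What is at stake is the internal agreement of three figures: the number required, the expected loss and the enrolment target. If the loss turns out exactly as the protocol expects, the trial ends slightly below the size that the protocol calls necessary for its stated 80% power.

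**Working it through.** **Inputs**

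- Required evaluable number: 40 per group, 80 in total (Subjects item 1).
- Expected loss: 10% (Subjects item 2; Statistical Considerations item 3).
- Enrolment: 44 per group, 88 in total (Subjects item 3; Statistical Considerations item 3).
- Mean 13.5 (unit not printed, taken as days), SD 11.7, difference 6 days, two-sided 5%, unequal-variance t-test, common coefficient of variation (Statistical Considerations item 3).
- Equal allocation (Statistical Considerations item 1).
- Inferred: the second mean is 13.5 - 6 = 7.5 days. The protocol does not print it.

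**Step 1: reproduce the base number**

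The coefficient of variation is 11.7/13.5 = 0.867, so the SD at a mean of 7.5 is 0.867 x 7.5 = 6.5. With n per group, the standard error is √((11.7² + 6.5²)/n) = √(179.14/n). The noncentrality is 6 divided by that standard error, and the degrees of freedom follow Satterthwaite.

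At n = 40 the standard error is √4.4785 = 2.116, the noncentrality is 2.835 and there are about 61 degrees of freedom. Power from the noncentral t distribution is 79.7%, which agrees with the stated 80%. The other readings of a 6-day difference do not reproduce it: 13.5 against 19.5 days gives 44%, and 16.5 against 10.5 days gives 60%.

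**Step 2: apply the loss to the planned enrolment**

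- Per group: 44 x 0.90 = 39.6, against 40 required.
- In total: 88 x 0.90 = 79.2, against 80 required, a shortfall of 0.8.

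**Step 3: find the enrolment that meets the requirement**

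- Per group: 40/0.90 = 44.4, rounded up to 45. Expected evaluable: 45 x 0.90 = 40.5.
- In total: 80/0.90 = 88.9, rounded up to 89, or 90 with equal groups. Expected evaluable at 90: 81.

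Two routes lead to the printed 44: 40 x 1.10 = 44, and 40/0.90 = 44.4 rounded to the nearest whole number. Both leave 39.6.

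**Step 4: cost in power, same method as step 1**

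| Evaluable per group | Enrolled per group (10% loss) | Power |
|---|---|---|
| 39.6 | 44 | 79.3% |
| 40 | 44.4 | 79.7% |
| 40.5 | 45 | 80.2% |

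The shortfall costs 79.7 - 79.3 = 0.4 percentage points.

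**The case against.** The strongest reply is that this is rounding and nothing more. The shortfall is under one infant in the whole trial. The 10% is an anticipated rate and not a fixed count: if 8 of 88 are lost (9.1%), exactly 80 remain. The mean and SD come from 8 neonates, so 0.4 points of power is far below the uncertainty in the inputs. All of this stands, and it is why the point is minor. It does not make the printed figures agree at the loss rate the protocol itself states.

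A reader might go further in three ways that the document does not support.

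- **That a wrong inflation formula was used.** The number 44 fits multiplication by 1.10, but it also fits division by 0.90 followed by rounding to the nearest whole number. With no formula printed, the two cannot be told apart.
- **That the 10% covers only ECMO and prolonged CPR, so true loss must be higher.** Subjects item 2 names these as included among post-operative complications, so the list is not exhaustive. Infants still intubated at two weeks, who are also excluded, may already be counted in the 10%. The protocol gives no figure for a higher loss.
- **That the trial is likely to fail because both groups must each retain 40.** The protocol sets no such criterion. An allowance based on expected loss does not guarantee a minimum: if each infant has a 10% chance of loss, even 45 per group would leave both groups at 40 or more only about half the time.

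**Conclusion.** The point holds as a minor correction. At the protocol's own 10% loss, 44 per group is expected to leave 39.6 evaluable (79.2 in total), just below the 40 (80 in total) called necessary. This follows from the printed figures alone and does not depend on how 44 was obtained.

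The power figures, 79.3% against 79.7%, rest on the inferred mean of 7.5 days and a common coefficient of variation of 0.867. That reading is credible because it reproduces the stated 80%. It would be wrong to conclude that the trial is materially underpowered on this account: the difference is 0.4 percentage points, and the planned enrolment is one infant per group below the rounded-up figure.

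**What to change.** Keep enrolment at 88 and make the text agree with it. In Human Participants, Subjects items 1 and 2, and in Statistical Considerations item 3, state that with 88 enrolled and 10% lost about 79 infants are expected to be evaluable, with power of about 79% for a 6-day difference. Print the second mean and the inflation formula with its rounding rule, so that a reader can repeat the calculation. Items 3 and 4 can stay at 88. The cost is a few sentences and a stated power about one point lower, with no change to conduct.

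Optionally, round up to 45 per group, 90 in total. Expected evaluable numbers are then 40.5 per group with power of 80.2%, so the stated 40 and 80% can remain. The cost is two more infants and a change of 44 to 45 and 88 to 90 in Subjects items 3 and 4 and in Statistical Considerations item 3.

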Study Title: Nasal vs. Oral Intubation for Neonates Requiring Cardiac Surgery

University of Virginia IRB for Health Sciences Research Protocol #20789

Principle Investigator: [name]

Document Type: Protocol

Document Date: 6/14/18

PROTOCOL

Background

1. Provide the scientific background, rationale and relevance of this project.

Neonates requiring cardiac surgery early in infancy frequently develop feeding difficulties including problems reaching full volume nutrition and transitioning to oral feeds. This is a particular challenge because adequate nutrition status is associated with improved outcomes for these patients. Feeding difficulties are multifactorial, and may arise due to prolonged post-operative intubation, surgical complications, or delay in initiating enteral nutrition. This results in longer hospitalizations, and need for invasive feeding interventions like nasogastric or gastrostomy tube feedings.

Kogon et al. (2007) conducted a retrospective review of 83 infants requiring cardiac surgery in their first 15 days of life. They found that 44.6% of these infants had difficulty transitioning from gavage to oral feeds. 9.6% of infants required invasive procedures (gastrostomy tube, Nissen fundoplication) to facilitate feeding. They identified increased risk adjusted congenital heart surgery (RACHS) score and prolonged intubation as risk factors for delayed transition and need for additional feeding procedures. Single ventricle physiology and presence of a shunt were additionally identified as risk factors for additional feeding procedures.

Piggott et all (2018) conducted a retrospective review of 79 neonates who required the Norwood procedure for congenital heart disease in their first 30 days of life. Of these patients, 59.5% required gastrostomy tube placement for feeding before discharge. They identified vocal cord dysfunction and longer duration of postoperative sedative/narcotic infusion as risk factors for gastrostomy tube placement. Patients who required gastrostomy feedings had a significantly longer hospital length of stay.

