Skinner et al. (2005) conducted fiberoptic laryngoscopy in 33 neonates after Norwood single ventricle palliation compared with 18 infants after aortic arch reconstruction as part of biventricular repair. In the Norwood group, 48% of infants had some degree of swallowing dysfunction. 9% of Norwood infants were diagnosed with left vocal cord paralysis, 24% had aspiration on barium swallow, and 18% of infants required gastrostomy tube placement for feeding. In the aortic arch reconstruction group, 25% of infants were diagnosed with left vocal cord paralysis, 35% had aspiration on barium swallow, and 11% required gastrostomy tube placement for feeding. They concluded that vocal cord paralysis and aspiration occur in similar frequencies in neonates regardless of single or biventricular repair.

Both oral and nasal intubation routes are considered safe and acceptable in neonates. However, there have been only a few head-to-head trials to compare the two routes to each other in this population. Spitzer et al. (1982) conducted a trial of 86 neonates requiring intubation for mechanical ventilation. Infants were randomized to oral or nasal routes of intubation. The study found that nasally intubated infants had higher rates of post-extubation atelectasis. However, after accounting for weight, they found that the higher risk of post-extubation atelectasis was only present in infants < 1500 grams. Infants > 2500 grams (term size) were not at higher risk of post-extubation atelectasis. There was not a difference in the risk of local trauma (nasal erosions for nasal intubation, palatal groove formation for oral intubation) between groups. McMillan et al. (1986) conducted a trial of 91 neonates requiring intubation for mechanical ventilation. Infants were randomized to oral or nasal routes of intubation. In this study, nasal intubation was unsuccessful in 6 patients, who were subsequently successfully orally intubated without complications. They did not find increased risk of post-extubation atelectasis, endotracheal tube blockage, or accidental extubation in nasal compared to oral routes of intubation.

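### The primary null, t-test and negative binomial model need a day count for every infant, but infants discharged on tube feeds have none

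*Protocol*

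**What the plan says.** Under Objectives/Hypothesis, the single primary outcome is the time from surgery to full oral feeds. Statistical Considerations, item 2, sets the null that "the mean number of days to full oral feeding is the same with oral or nasal intubation", against a two-sided alternative. Item 4 fixes the methods: "Initial analyses will use the two-sample t-test, and the associated confidence interval, to compare the groups". Secondary analyses of "the number of days until full oral feeding, will be based on negative binomial regression", unadjusted and adjusted for covariates such as the RACHS score. Item 3 gives 80% power for the unequal-variance t-test with 40 per group and a 6-day difference, raised to 44 per group for 10% dropout.

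Study Procedures, item 1, ends follow-up: "Data will be collected through hospital discharge". Secondary outcome 3 is "Need for tube feeds at discharge (NG or gastrostomy"), compared by chi-square.

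Human Participants, item 2, expects 10% of infants to be unobserved on the primary outcome. It attributes this to post-operative complications, with ECMO and CPR over 5 minutes as examples. Tube feeding at discharge is not mentioned there. No section gives a tube-fed infant a number of days, censors that infant or ranks that infant.

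**The concern.** Full oral feeding is an event that some infants will not reach before discharge. The protocol foresees this, because it counts such infants in a secondary outcome. A mean, a t-test and a negative binomial model on days, as described, all need a completed count from each infant.

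The protocol's Background suggests these infants may not be rare. In one series operated on in the first 15 days of life, "9.6% of infants required invasive procedures (gastrostomy tube, Nissen fundoplication) to facilitate feeding". In a Norwood series "59.5% required gastrostomy tube placement for feeding before discharge", and in a second Norwood series "18% of infants required gastrostomy tube placement for feeding". An arch-reconstruction group had 11%.

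The obvious default in software is to leave out infants with no value. That would select on something that happens after randomisation and that the intervention is meant to change, since the rationale is that nasal intubation helps infants avoid gastrostomy. The primary comparison would then no longer be between the groups as randomised. It could shrink a real benefit or turn one into apparent harm.

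**Working it through.** **The protocol's own figure.** Inputs from Statistical Considerations, item 3: mean 13.5, SD 11.7 (8 infants, time to NG tube removal), difference 6 days, equal coefficient of variation, 40 per group, two-sided 5%.

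- CV = 11.7 / 13.5 = 0.867, so at a mean of 7.5 the SD is 0.867 × 7.5 = 6.5.
- SE = √(11.7²/40 + 6.5²/40) = √(3.422 + 1.056) = 2.116.
- Noncentrality = 6 / 2.116 = 2.835, with Satterthwaite df = 61.
- Power = 79.7% (noncentral t), or 80.9% (normal approximation).

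The stated 80% reproduces, but only if all 40 per group have a number of days.

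**What happens if infants without a value are dropped.** Assumptions: gamma feeding times with the means and CV above (shape 1/0.867² = 1.33), 40 per arm, 20,000 simulated trials, Welch test. With complete data this simulation has about 83% power, slightly above the 79.7% formula value because the times are skewed. The oral-arm rates of 9.6% and 18% come from the Background and describe other cohorts.

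| Scenario | No value, oral vs nasal | Difference after dropping | Result of the t-test |
|---|---|---|---|
| 1. Slowest infants have no value; true difference 6 days | 9.6% vs 1.1% (beyond day 29.4) | 3.5 days | 60% power |
| | 18% vs 3.6% (beyond day 22.4) | 2.4 days | 43% power |
| 2. Equal loss, unrelated to speed; true difference 6 days | 9.6% in both | 6.0 days | 79% power |
| | 18% in both | 6.0 days | 75% power |
| 3. Equal speed (both means 13.5), but half of the slow nasal infants reach oral feeds instead of leaving on tubes | 9.6% vs 4.8% | −1.5 days (nasal slower) | significant against nasal in 9% of trials |
| | 18% vs 9% | −2.4 days (nasal slower) | significant against nasal in 20% of trials |

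In scenario 3 the nominal rate of significance against nasal would be 2.5%.

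**A milder version of scenario 1.** Here discharge times are independent of feeding times (gamma, CV 0.6, assumed; 4,000 trials) and the true difference is again 6 days.

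- 9% oral and 3% nasal tube-fed at discharge: dropping gives 4.6 days and 70% power. Entering the discharge day as if it were the event day gives 5.2 days and 80%.
- 32% and 15% tube-fed: dropping gives 2.6 days and 39%. The discharge day gives 3.3 days and 67%.

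The same trial therefore yields different effects and different power according to a choice the protocol does not make.

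**The case against.** The strongest reply is that this is a rule for the statistical analysis plan. The t-test can be used once infants not reaching full oral feeds are assigned a day. The protocol never says that they are dropped, so the bias shown follows from an assumed choice. The second half is right, and the figures are conditional for that reason. The first half does not hold. The protocol itself fixes the null, the test, the model, the end of data collection and the power. Assigning a day changes the null to a restricted mean and changes the power, so the protocol text would still have to change.

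It can also be said that the rates are borrowed. They count gastrostomy or invasive procedures, two come from Norwood infants only, and this trial's exclusions may remove poor feeders. That stands, and the true rate could be lower. It could also be higher, because the cited rates do not count infants sent home on NG feeds and secondary outcome 3 does.

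Scenario 1 is a worst case, since everyone past one cutoff lacks a value and nobody else does. The independent-discharge version is milder. Scenario 1 is also overstated if the pilot mean, measured to NG removal, already describes only infants whose tube came out. Scenario 3 depends on the rescued nasal infants reaching feeds late but still in hospital. These limits affect the size, not the existence, of the problem.

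The 10% allowance is not a closed list, but it names complications and not tube-fed discharge. The chi-square test does count these infants, but only as a secondary outcome.

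**Conclusion.** The concern holds and must be fixed before outcome data are compared. The null and both methods for the primary outcome do not fit an event that some infants will not reach before data collection ends. That conclusion comes from the text alone.

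The size is illustrative, because the trial's own rate of tube-fed discharge is not given. At oral-arm rates of 9.6% or 18%, dropping infants without a value ranges from almost harmless (6.0 days; 79% or 75% power), through heavy shrinkage (3.5 or 2.4 days; 60% or 43% power), to a reversed sign (−1.5 or −2.4 days). Which of these applies depends on why infants lack a value and on whether that differs by arm. The sample size arithmetic itself is correct for complete data.

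**What to change.** Rewrite Statistical Considerations, items 2 to 4, so that the primary analysis keeps every infant in the analysis set and the null matches it. There are three workable options:

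- (a) Cumulative incidence of full oral feeding from surgery, with tube-fed discharge (and death, if any) as competing events. Compare by Gray's test, with a subdistribution hazard model including the RACHS score.
- (b) A Wilcoxon rank-sum test with infants not reaching full oral feeds given the worst rank.
- (c) The smallest change: keep the t-test, give infants not reaching full oral feeds before discharge one stated common day D, and cap all values at D. The null becomes equality of mean days to full oral feeding restricted to day D. The RACHS-adjusted model uses the same values with robust standard errors.

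Report mean days among infants who reach full oral feeds as descriptive only. Restate power for the chosen analysis over a range of tube-fed discharge rates, equal and unequal between arms.

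No new data are needed, but 80% power at 40 per arm should not be claimed as kept. Power for a true 6-day difference, at oral-arm rates of 9.6% / 18%:

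| Analysis | Slowest infants without a value | Equal loss unrelated to speed |
|---|---|---|
| Gray's test | 84% / 82% | 38% / 23% |
| Worst rank | 75% / 74% | 56% / 42% |
| t-test, common day 28 | 82% / 81% | 58% / 44% |
| t-test, infants dropped | 60% / 43% | 79% / 75% |

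Type I error with equal arms is 4.8% to 5.3% for the three options. In scenario 3 they largely remove the false signal against nasal intubation, but they reject in only about 5% to 8% of trials, so they would seldom detect that kind of benefit at this size. Under (a) or (b) the headline is no longer a mean difference in days. Under (c) it depends on D (at 9.6% equal loss, 62% power at day 21 and 51% at day 35), and tube-fed infants receive that day although feeding after discharge is not observed. The sponsor may have to accept lower power or enrol more infants.
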